## **Study procedures**

Subjects identified with COPD will be informed about the study and invited to participate by investigators at the time of their routine control visits. All therapies will be prescribed according to the updated National COPD Guidelines (GesEPOC) indicating among other therapies active reduction of risk factors, influenza and pneumococcal vaccination (with PCV13) in all patients with mild, moderate or severe COPD. All the patients will be counselled to stop smoking and advised on life-style modifications. Any vaccination will be prescribed according to clinical practice and not related to the decision to include the subjects in the study. Subjects may be vaccinated before or after inclusion in the study.

Study will include periodic scheduled visits for all patients, to complete a total follow up of 2 years (see Table 1).

### **8.2.1. Inclusion criteria**

Patients must meet all of the following inclusion criteria to be eligible for inclusion in the study:

1. Patient  $\geq 18$  years diagnosed with COPD (any stage, the subgroups for the analysis would be based on COPD severity grade)

Redacted

2. Evidence of a personally signed and dated informed consent document indicating that the patient (or a legally acceptable representative) has been informed of all pertinent aspects of the study.
3. Ability to understand and complete the required QoL questionnaires
4. At least 2 years of clinical history available that includes records of previous moderate/severe exacerbations, influenza and pneumococcal vaccination history comorbidities and previous treatments.
5. Spirometry data\* (maximum 6 months old, or if not available at enrollment, to be performed as per normal clinical practice at visit 1 +/- one month)

\*Subjects with FEV1 <40 should be less than 20% of the total study population (related to the microbiological etiology dependent on severity)

### **8.2.2. Exclusion criteria**

Patients meeting any of the following criteria will not be included in the study:

1. Impossibility to perform prospective follow up
2. Present any immunocompromising condition
3. Present any other respiratory diseases as co-morbidity (subjects with overlap syndromes COPD-asthma will be excluded. Mixed phenotype defined as: symptoms of increased variability of airflow and incompletely reversible airflow obstruction)

### **8.3. Variables**

**Variables to be recorded from previous clinical history and follow up visits (according to Table 1):**

- Consent date
- Subject code
- Demographic and epidemiological data;
- Antropometric data (weight, height, body mass index (BMI), Waist Circumference)
- Smoking habit, alcohol consumption
- Spirometric data (FEV1, FVC, FEV1/FVC)
- Pharmacological treatment
- COPD severity (GOLD)
  - o GRADE 1: Mild/unknown [FEV1≤ 80%, FEV1/FVC < 0,7 or no spirometry data]
  - o GRADE 2: Moderate [50% ≤ FEV1< 80%,FEV1/FVC < 0,7]
  - o GRADE 3: Severe [30% ≤ FEV1 < 50%, FEV1/FVC < 0,7]
  - o GRADE 4: Very severe [FEV1< 30% o FEV1< 50% plus respiratory failure,FEV1/FVC < 0,7]
- Number and severity of exacerbations

Redacted

- Frequency of total exacerbations (moderate and severe) in the previous year and during follow-up (recorded at hospital or primary care level).
- Comorbidities
  - o high blood pressure
  - o dyslipidemia
  - o type 2 diabetes mellitus
  - o metabolic syndrome
  - o heart failure
  - o ischemic heart disease
  - o chronic kidney disease
  - o cirrhosis
- History of neoplasia (solid organ and hematologic)
- Pneumococcal vaccination
- Influenza vaccination
- QoL questionnaire (reduced SGRQ, CAT) - completed by subjects and transcribed into electronic case report form (CRF)

### **8.3.1 Study procedures**

#### **Visit 0: selection and recruitment**

- Obtain of signed informed consent document
- Confirmation of eligibility
- Assignment of subject number. Subject number will be assigned sequentially as the participants are included in the study. The number will be composed of 6 digits, first three will be the site code and last three the subject number.

Study authorized personnel will complete the case report form (CRF) for each of the subjects included. CRF (Annex 2) will be completed by an interview of the subject or review of clinical history and results of test/activities performed (as part of routine clinical practice)

Redacted

**Visits 1 to 5: Follow Up**

Activities to be carried out in each of the follow up visits are detailed in Table 1

**TABLE 1. FOLLOW UP VISITS**

	Visit	0	1	2	3	4	5
	Month	0	1	6	12	18	24
Verification of inclusion/exclusion criteria		X	X	X	X	X	X
Informed consent signature		X					
Demographic variables		X					
Exacerbations and smoking history		X	X	X	X	X	X
Clinical history (hospital and/or primary care)		X					
Performance or verification of recent spirometry		X			X		X
Completion of QOL test		X			X		X
Treatment and vaccination recommendations adjustment (as per normal clinical practice)		X			X		X
Telephone Follow up (if applicable)				X		X	
PCV13 vaccination record			X		X		X
Influenza vaccination record			X		X		X
Updated treatment record			X		X		X

**Definitions:**

- COPD exacerbations are defined as a complex of two or more respiratory symptoms (worsening dyspnea, cough, sputum production, chest tightness, or wheezing) related to the underlying COPD, with duration of 3 days or more, that require a change in treatment.
  - *Treatment changes* include acute treatment with antibiotics and/or steroids, or an addition of new maintenance bronchodilator.
  - *Mild exacerbations* are those that require new prescription of bronchodilator only
  - *Moderate exacerbations* are those that require antibiotics and/or systemic corticosteroids without hospitalization,
  - *Severe exacerbations* are those that lead to hospitalization.
- The onset date of exacerbations is defined by the onset of the first recorded symptom.
- Exacerbations that occur within 7 days of onset of a prior exacerbation are counted as a single exacerbation

A subject presenting with exacerbation, will be considered as vaccinated at least 15 days after receiving immunization

Redacted

- Immunosuppression:
  - Lymphoma/Leukemia
  - Another neoplasm subjected to immunosuppressing treatments
  - Organ transplant with its corresponding immunosuppressing treatment
  - Leukopenia<1.000/mm; neutropenia<500/mm
  - Patients infected by Human Immunodeficiency Virus (HIV)
  - Congenital immunodeficiency
  - Diseases that requires continuous treatment with systemic corticosteroids administration for more than 14 days (prednisone at doses> 15 mg/day or other equivalent preparations), or cytotoxic agents during the previous six months.

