#### **8.5. Study size**

With 35% patients vaccinated with PCV13, enrolling 1540 eligible COPD patients will provide approximate 540 patients in PCV13 cohort and 1000 patients in the control cohort.

Assuming 37% of the control patients experiencing moderate/severe exacerbation per year with 70% of the patients remaining in the study at year 1, this sample size will provide 91% power to detect a statistical significant reduction of 10% on COPD moderate/severe exacerbations from PCV13 after 1-year. Assuming additional 30% dropout from year 2, the study sample size will provide 91% power to detect a statistical significant reduction of 14% on COPD moderate/severe exacerbations from PCV13 after 2-year.

Time	PCV13		Control		Power	Retention Rate
	Sample Size	% exacerbation	Sample Size	% exacerbation		
Enrollment	540		1000			
1-year	378	27%	700	37%	91.43%	70% from Enrollment
2-Year	264	60%	490	74%	91%	70% from Year 1

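### PCV13 and influenza doses are recorded at months 1, 12 and 24 but exacerbations at every contact, so some patients vaccinated after entry and then lost may be counted as unexposed

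*Protocol*

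**What the plan says.** Protocol Table 1 (Section 8.3.1) ticks the rows "PCV13 vaccination record" and "Influenza vaccination record" at visits 1, 3 and 5, that is months 1, 12 and 24. The row "Exacerbations and smoking history" is ticked at all six contacts: months 0, 1, 6, 12, 18 and 24. Months 6 and 18 are the telephone contacts. Clinical history from the hospital or primary care is ticked at visit 0 only. No row covers PPV23. Section 8.3 lists pneumococcal vaccination among the variables, without naming the product, and refers to Table 1 for the timing.

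The Study procedures text under Protocol 8.2 says: "Subjects may be vaccinated before or after inclusion in the study". The definitions below Table 1 count a patient as vaccinated from 15 days after the dose. Section 8.5 assumes "70% of the patients remaining in the study at year 1" and a further 30% dropout in year 2.

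The SAP has two exposure classes, vaccinated or not vaccinated with PCV13 (Sections 5.4, 8.1 and 8.2.1). It analyses all evaluable patients (5.1) and runs exacerbation rates to the last follow-up visit (8.2.3.1). Outside the SGRQ it replaces no missing values (Section 7). It has no rule for a patient whose vaccine status is unknown at the last contact. If numbers allow, SAP 8.2.1 splits exposed patients by PCV13 alone, with PPV23, with influenza vaccine, or with both.

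**The concern.** The main exposure is recorded less often than the outcome. For a dose given after month 1, entry to the exposed group depends on reaching month 12 or month 24. A patient who is vaccinated, reports exacerbations by telephone and is then lost leaves events and follow-up time on file, but no scheduled record of the dose.

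If absence of a record is read as absence of vaccination, the patient joins the comparator with events that occurred after vaccination. The error depends on retention, so it is not random: it favours completers in the exposed group and puts vaccinated time into the control group. The same patient also drops out of the SAP's paired comparison of rates before and after PCV13. Protocol 8.9 already accepts that losses to follow-up can bias the results.

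**Working it through.** **1. The plan's own figures.** Retained numbers: 540 × 0.7 = 378 and 1000 × 0.7 = 700 at year 1; 378 × 0.7 = 264.6 (plan: 264) and 700 × 0.7 = 490 at year 2. Year-1 power for 27% against 37% (pooled variance, two-sided 0.05; the sidedness is my assumption):

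- pooled proportion = (378 × 0.27 + 700 × 0.37)/1078 = 0.335
- null standard error = 0.0301; alternative standard error = 0.0292
- z = (0.10 − 1.96 × 0.0301)/0.0292 = 1.40, so power is 91.9%, against 91.43% stated.

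The year-1 figure reproduces. The same formula gives 97.5% at year 2 against 91% stated; that is a separate matter. Both figures use patients retained to months 12 and 24, when the vaccine record is taken, so this gap does not alter them.

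**2. Who is affected.** Follow-up time ends at the last visit, so there are three cases:

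- Dosed, then attends month 12 or 24: the dose can be captured there.
- Dosed after the last contact, then lost: no time or events after the dose are on file, so unexposed is correct for the observed time.
- Dosed in months 1-6 (or 12-18), contacted at month 6 (or 18), then lost before month 12 (or 24): exacerbations are on file and the dose is not. Only this case does harm.

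**3. How many.** Assumptions: constant loss at 70% retention per year, and doses spread evenly over months 1-24 among patients still followed. The documents do not give the timing of doses.

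S(t) = 0.7^(t/12), so S(1) = 0.9707, S(6) = 0.8367, S(12) = 0.7000, S(18) = 0.5857, S(24) = 0.4900. Monthly hazard λ = −ln(0.7)/12 = 0.02972.

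- All doses after month 1: [S(1) − S(24)]/λ = 0.4807/0.02972 = 16.17
- Harmful, first window: 5 months × [S(6) − S(12)] = 5 × 0.1367 = 0.683
- Harmful, second window: 6 months × [S(18) − S(24)] = 6 × 0.0957 = 0.574
- Harmful share: (0.683 + 0.574)/16.17 = **7.8%**
- Doses within the two windows: (0.9707 − 0.8367)/λ + (0.7000 − 0.5857)/λ = 4.51 + 3.85 = 8.36; harmful share of these = 1.257/8.36 = **15%**

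For comparison, everyone lost before the next vaccine record: months 1-12 give 9.108 − 11 × 0.70 = 1.408; months 12-24 give 7.065 − 12 × 0.49 = 1.185; the total is 2.593/16.17 = 16.0%. The remaining 8.3% had no contact after the dose.

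**4. Effect on the contrast (illustration).** Under constant loss, 13.7% of enrolled patients are lost between months 6 and 12. Suppose 10%, 20% or 50% of the 540 vaccinees are dosed in months 1-6. Then 540 × share × 0.137 gives about 7, 15 or 37 patients moved to the 1000 controls, each carrying the plan's 27% risk.

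| Dosed in months 1-6 | Moved | Control risk | Difference from 27% |
|---|---|---|---|
| none | 0 | 37.0% | 10.0 points |
| 10% | 7 | (370 + 7 × 0.27)/1007 = 36.9% | 9.9 points |
| 20% | 15 | (370 + 15 × 0.27)/1015 = 36.9% | 9.9 points |
| 50% | 37 | (370 + 37 × 0.27)/1037 = 36.6% | 9.6 points |

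This gives lost patients the same risk as other vaccinees. If their risk differs, the shift differs too.

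**The case against.** A dose can be recovered without a tick at month 6 or 18. Protocol 8.4 names medical records as a data source, Section 8.3.1 lets the CRF be completed from the clinical history, and Section 8.2 says specialists may use the primary care database. Section 9.2 states that loss to follow-up is not withdrawal. The CRF is not among the documents and may ask for product and date. Vaccination recommendations are reviewed at months 0, 12 and 24, and a vaccine record at month 1 follows the first, so many doses may be caught early. All of this stands, and it limits the size of the problem. But chart access is optional, and nothing requires a vaccine search at months 6 or 18 or when a patient is lost. Uptake after the month-12 recommendation is next recorded only at month 24.

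A reader might infer that patients vaccinated and lost between visits are in fact analysed as unexposed. No section says so: the SAP defines unexposed as not vaccinated with PCV13, not as having no vaccine record, and is silent on unknown status. A reader might also take the 16% as the error. About half of it concerns patients with no contact after the dose, whose observed time is correctly unexposed.

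Nor does the missing PPV23 row change who is unexposed to PCV13. It bears only on the SAP's vaccine subgroups, which are conditional on sufficient numbers.

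**Conclusion.** The point holds in a limited form. Patients dosed in months 1-6 or 12-18, contacted at month 6 or 18 and lost before the next vaccine record may be counted as unexposed. That is about 8% of those vaccinated after month 1, or about 15% of those dosed in the two windows, given 70% yearly retention, constant loss and even dosing. The effect on the overall contrast is probably small and scales with the share vaccinated after entry, which the documents do not give. The stated power is unchanged. Separately, PPV23 given after entry has no scheduled record, so patients could be misassigned between the PCV13-only and PCV13 plus PPV23 subgroups. This is a cheap improvement worth making, not a threat to the main comparison.

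**What to change.** - **Table 1:** replace the PCV13 row with *pneumococcal vaccination record (product PCV13/PPV23, date)*. Tick it, and the influenza row with date, at visits 2 and 4 as well as 1, 3 and 5.
- **Loss to follow-up:** for patients lost without withdrawing consent, take vaccine dates from the hospital or primary care record up to the last contact.
- **SAP:** state that patients with no vaccine information up to their last contact are not classed as unexposed by default.

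Under the model above, the harmful share falls from about 8% to about 0%, provided the month 6 and 18 contacts take place and the dose is reported. The cost is a few questions at existing telephone contacts, a revised eCRF page, a record search for lost patients and a sentence in the SAP; no visit or procedure is added. The drawback is that dates given by telephone are self-reported and need checking against the record.

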#### **8.4. Data sources**

For this study, data source will include medical records, emergency room reports, QoL questionnaires and the electronic case report form (CRF).

#### **8.5. Study size**

With 35% patients vaccinated with PCV13, enrolling 1540 eligible COPD patients will provide approximate 540 patients in PCV13 cohort and 1000 patients in the control cohort.

Assuming 37% of the control patients experiencing moderate/severe exacerbation per year with 70% of the patients remaining in the study at year 1, this sample size will provide 91% power to detect a statistical significant reduction of 10% on COPD moderate/severe exacerbations from PCV13 after 1-year. Assuming additional 30% dropout from year 2, the study sample size will provide 91% power to detect a statistical significant reduction of 14% on COPD moderate/severe exacerbations from PCV13 after 2-year.

Time	PCV13		Control		Power	Retention Rate
	Sample Size	% exacerbation	Sample Size	% exacerbation		
Enrollment	540		1000			
1-year	378	27%	700	37%	91.43%	70% from Enrollment
2-Year	264	60%	490	74%	91%	70% from Year 1

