### **8.9. Limitations of the research methods**

- The actual proportion of subjects who would follow their healthcare practitioner (HCP) vaccination recommendation is not known, so this aspect might influence the size of the vaccinated group and therefore the global results.
- Losses to follow-up can introduce bias in the global results obtained.
- Considering the bacterial etiology depending on disease severity, a very large percentage of patients with  $FEV_1 < 40\%$ , would limit the proportion of *S.pneumoniae* presence in the study population and hence the potential impact of the immunization.
- The estimated study sample, aims to determine if there is a 10% significant reduction on the risk of all cause COPD exacerbations in PCV13 vaccinated subjects. Since there is no previous evidence to guide the reduction magnitude, this may be a potential limitation considering that experience with PCV13, coming from a large clinical trial including over 84,000 subjects only found a 5% (non-significant) reduction on all cause CAP and in addition, the proportion of vaccine type infection in COPD exacerbations is not established. However, recent pilot studies results showed a significant reduction on total number of exacerbations in a small group of 90 subjects 2 years post-vaccination.

Redacted

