5 ANALYSIS SYSTEMS / POPULATIONS

Considering that 37% of COPD patients will have one moderate/severe exacerbation per year, and assuming that at least 35% of patients will follow their doctor's vaccination

recommendation,³ to have at least 200 vaccinated COPD patients with moderate/severe exacerbations, a total of 1541 eligible subjects should be included in the analysis.

With 35% of patients vaccinated with PCV13, enrolling 1541 eligible subjects with COPD would provide approximately 540 patients in the PCV13 cohort and 1000 patients in the unexposed cohort.

Assuming that 37% of unexposed patients will present one moderate/severe exacerbation per year,² with 70% of the patients remaining in the study after 1 year, this sample size would provide 91% power to detect a statistically significant reduction of 10% in moderate/severe COPD exacerbations with PCV13 after 1 year. Assuming an additional 30% dropout in the second year, the study sample size would provide 91% power to detect a statistically significant reduction of 14% in moderate/severe COPD exacerbations with PCV13 after 2 years.

Time	PCV13		Unexposed		Power	Retention rate
	Sample size	% exacerbation	Sample size	% exacerbation		
Enrollment	540		1000			
1 year	378	27%	700	37%	91.43%	70% from enrollment
2 years	264	60%	490	74%	91%	70% from year 1

5.1 **FULL ANALYSIS**

The statistical analysis of this study will be carried out with all those evaluable patients with COPD, recruited by the Spanish sites participating in the study and who meet the following selection criteria:

5.1.1 **Inclusion Criteria**

Patients must meet all of the following inclusion criteria to be eligible for inclusion in the study:

1. *Aged 18 years or older at the time consent is given*
2. *Patient diagnosed with COPD (any stage, subgroups for analysis will be based on COPD severity)*
3. *Evidence of a personally signed and dated informed consent document indicating that the patient has been informed of all pertinent aspects of the study.*
4. *Ability to understand and complete the required quality of life questionnaires*
5. *Patients with at least 2 years of previous clinical history available relating to (if applicable) history of moderate/severe exacerbations, influenza and pneumococcal vaccination history, comorbidities and previous treatments*
6. *Spirometry data* (maximum 6 months old, or if not available at enrollment, to be performed as per normal clinical practice at visit 1 ± one month)*

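### The 10% and 14% reductions behind the power claim are percentage points (27% and 19% relative), and Protocol 8.9 compares the 10% with a benchmark that can only be relative

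*Protocol*

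**What the plan says.** Protocol 8.5 makes two power statements. At 1 year the study has "91% power to detect a statistical significant reduction of 10% on COPD moderate/severe exacerbations from PCV13 after 1-year". At 2 years it has "91% power to detect a statistical significant reduction of 14% on COPD moderate/severe exacerbations from PCV13 after 2-year". SAP section 5 says the same in almost the same words ("91% power to detect a statistically significant reduction of 10% in moderate/severe COPD exacerbations with PCV13 after 1 year"). Neither document says whether these are absolute or relative reductions.

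The table below the text, identical in both documents apart from the label of the control group, gives the rates:

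- 1 year: 27% of 378 vaccinated against 37% of 700 controls, power 91.43%
- 2 years: 60% of 264 against 74% of 490, power 91%

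Protocol 8.9 returns to the effect size and shows no rates. The sample, it says, "aims to determine if there is a 10% significant reduction on the risk of all cause COPD exacerbations in PCV13 vaccinated subjects". It calls this a possible limitation, because a large PCV13 trial in over 84,000 subjects "only found a 5% (non-significant) reduction on all cause CAP" and because the share of vaccine-type infection in exacerbations is not known. It then points to small pilot studies with significant reductions. The primary objective (Protocol section 7, SAP 2.2) is set at 2 years of follow-up.

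**The concern.** A reduction of 10% in a risk is usually read as relative. On that reading a 37% control rate falls to 33.3%, and the stated power does not apply.

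Protocol 8.9 turns the missing label into a matter of substance. It is the one place where the plan weighs whether its assumed effect is plausible, and it sets a difference in percentage points beside what appears to be a relative reduction. An ethics committee or later reader would take the assumption to be about twice the large-trial result. If the study finds no difference, a reader relying on 91% power for a 10% reduction in risk would count that as strong evidence against an effect the study was not sized to detect.

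**Working it through.** **Inputs.** Rates, group sizes and stated power come from the tables in Protocol 8.5 and SAP section 5. The significance level is 0.05 (SAP section 4). Its sidedness is not stated, so two-sided is assumed. The benchmark is the 5% non-significant reduction in over 84,000 subjects from Protocol 8.9.

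**1. Reproduce the 1-year power.** For 27% of 378 against 37% of 700, Fisher's exact test by full enumeration gives 91.44%, against the stated 91.43%. The pooled normal approximation gives 91.9%. The stated figure therefore belongs to a difference of 10 percentage points.

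**2. Convert to the relative scale.** Relative reduction = 1 − (rate in vaccinated ÷ rate in controls).

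- 1 year: 1 − 27/37 = 27.0%
- 2 years: 1 − 60/74 = 18.9%

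**3. Find the scale of the 5% benchmark.** Suppose it were 5 percentage points. With 84,000 subjects in equal arms (an assumption) and the largest possible binomial variance, 0.25, the standard error is √(0.25 × (1/42,000 + 1/42,000)) = 0.00345. Then z = 0.05/0.00345 = 14.5, and any other event rate makes z larger. At 1:9 allocation the standard error is 0.00575 and z is 8.7. Such a difference could not be non-significant, so the 5% is relative.

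**4. Compare like with like.**

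| Comparison | Ratio to the 5% benchmark |
|---|---|
| As the figures stand in 8.9 | 10/5 = 2.0 |
| 1 year, relative | 27.0/5 = 5.4 |
| 2 years, relative | 18.9/5 = 3.8 |

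**5. Power if the reduction were truly relative** (Fisher exact, two-sided 0.05, group sizes from the tables).

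| Relative reduction | 1 year (378 v 700) | 2 years (264 v 490) |
|---|---|---|
| 10% | 33.3% v 37%: 21.7% | 66.6% v 74%: 55.5% |
| 5% | 35.15% v 37%: 8.7% | 70.3% v 74%: 18.4% |

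**6. Check the 2-year power.** For 60% of 264 against 74% of 490, Fisher's exact test gives 97.3% and the pooled normal approximation 97.5%. The stated 91% is lower than its own inputs give. Reading the 14% as relative does not explain it either: 63.6% against 74% gives 83.9% (pooled normal).

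**The case against.** The strongest reply is that the scale can be recovered where the power is claimed. The table under the sentence shows both rates, and the 1-year power is right for them. This stands. A reader might infer from the wording that the 91% is false or miscalculated, and the documents do not support that. The fault at 1 year is an unlabelled scale. The reply does not rescue Protocol 8.9, which has no rates and makes the comparison across scales.

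Second, 8.9 already concedes that the assumed effect may be too large, and it nowhere states a ratio of two. That ratio is what a reader would draw from the adjacent figures. The admission is genuine, but the comparison offered with it understates the gap.

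Third, the benchmark is not the only earlier evidence, and its endpoint is CAP rather than exacerbations. Protocol section 6 cites a 50% reduction in severe exacerbations in the second year among 90 vaccinated patients, and a 4.8-fold reduction in the incidence of exacerbations in a group of 25. Both exceed 27%. It would therefore be wrong to infer that the assumption goes beyond all prior evidence. The protocol itself calls these results preliminary, and they do not justify comparing unlike scales with the one large trial it cites.

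Fourth, a headline of over five times is tempting. It is the 1-year ratio only; at the horizon of the primary objective the ratio is 3.8.

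Fifth, one might argue from biology that a 27% relative reduction is out of reach. Protocol 8.9 says that the vaccine-type share of exacerbations is not established, so the documents give no basis for a number.

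Finally, both documents plan 95% confidence intervals, which limits the risk of misreading a null result.

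**Conclusion.** The point holds as one of labelling and of a mixed-scale comparison, and it should be fixed. The planned effects are 10 and 14 percentage points, or 27% and 19% relative. Against the 5% relative benchmark that is 5.4 times at 1 year and 3.8 times at 2 years, where the text suggests 2. For a relative reduction of 10%, power is about 22% at 1 year and 56% at 2 years; for 5%, about 9% and 18%.

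These results assume a two-sided 0.05 test and the retained group sizes in the tables. That the benchmark is relative is inferred from its being non-significant in so large a trial; the protocol does not say so. The comparison is across endpoints, CAP against exacerbations, and is only as informative as that allows.

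Two smaller faults go with it. The 2-year power of 91% does not follow from its inputs, which give about 97%; that error runs against the sponsor's interest. And 8.9 refers to all-cause exacerbations with no severity, whereas 8.5 is calculated for moderate/severe ones and the definitions in 8.3.1 include a separate mild class. A reader might infer that *all cause* is itself the mistake. In its sentence it can be read as aetiology, in contrast to vaccine-type infection, so only the severity is missing.

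Nothing here shows that the sample size is wrong for the rates the plan assumes.

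**What to change.** 1. In Protocol 8.5 and SAP section 5, describe the effects as an absolute reduction of 10 percentage points (37% to 27%, relative reduction 27%) and of 14 percentage points (74% to 60%, relative reduction 19%).
2. In the same places, reconcile the stated 2-year power of 91% with its inputs, which give about 97% (Fisher exact, two-sided 0.05), and name the test and its sidedness.
3. Add the power at a 10% relative reduction (about 22% at 1 year, 56% at 2 years) and at 5% (about 9% and 18%).
4. In Protocol 8.9, make the comparison on the relative scale: 27% at 1 year and 19% at 2 years, against 5%. State that the benchmark endpoint is CAP.
5. In 8.9, add *moderate/severe* to the description of the exacerbations and keep *all cause*.

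The cost is a few sentences in three places. Enrolment, endpoints and analyses do not change. The 1-year power of 91% stays, and the added scenarios show how quickly power falls for smaller effects.
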